11.4. Evaluation Methods

11.4.1. Diagnosis

Eligible subjects will be indicated for tympanostomy tube placement in alignment with the Clinical Practice Guideline.¹ The Clinical Practice Guideline for tympanostomy tubes in children was developed by a multidisciplinary panel, to provide clinicians with evidence-based recommendations on patient selection and surgical indications for and management of tympanostomy tubes in children.

According to the Clinical Practice Guideline, the decision to perform unilateral or bilateral tympanostomy tube insertion when unilateral OME is present should be based on caregiver preference [to accept or decline the risk of a second surgical procedure] and the likelihood of persistent OME developing in the opposite ear. For AOM with presence of effusion, the Guideline recommends bilateral TT placement for unilateral or bilateral disease. With the current care paradigm, a physician may perform bilateral tube placement for a unilateral condition to avoid the risk of multiple OR procedures and general anesthesia exposures if the second ear becomes affected. Since this study procedure is conducted in-office, it is proposed that the decision to perform unilateral or bilateral TT placement for AOM with effusion be based on caregiver preference and physician clinical judgment regarding the likelihood of disease developing in the opposite ear, similar to the Guideline recommendation for chronic OME.

The indications for tube placement have been clarified (as noted in italics) in instances where unilateral placement may be deemed appropriate by the physician and acceptable by the parent/guardian. The clinical indications for tube placement for children include:

- Bilateral TT insertion for bilateral otitis media with effusion (OME) for 3 months or longer (chronic OME) and documented hearing difficulties;
- *Unilateral or bilateral* TT insertion for unilateral or bilateral OME, *respectively*, for 3 months or longer (chronic OME) and symptoms that are likely attributable to OME

that include, but are not limited to, vestibular problems, poor school performance, behavioral problems, ear discomfort, or reduced quality of life;

- *Unilateral or bilateral* TT insertion for recurrent acute otitis media (AOM) with unilateral or bilateral middle ear effusion at the time of assessment for tube candidacy, where recurrent AOM is defined as three or more AOM episodes in the past 6 months or at least 4 AOM episodes in the past 12 months with at least 1 in the past 6 months.
- *Unilateral or bilateral* TT insertion in at-risk children with unilateral or bilateral OME, *respectively*, that is unlikely to resolve quickly as reflected by a type B (flat) tympanogram or persistence of effusion for 3 months or longer (chronic OME). At risk children have increased risk for speech, language or learning problems from otitis media because of baseline sensory physical, cognitive or behavioral factors.

In this study, the caregiver will be informed of the risk of subsequent OME or AOM in the contralateral ear and the potential need for a second tube insertion procedure should this occur. Prior to procedure, the Investigator must document which ears are intended for in-office tube placement.

11.4.2. Concomitant Medications

All prior and concomitant medications will be recorded. Prior medications will include all prescription and over-the-counter medications taken up to 28 days before procedure. All concomitant medications, and changes to medications, will be recorded during each subject's study enrollment period. Medications may be prescribed based on Investigator's discretion, except for drugs or devices under investigation through a different protocol. Medications administered or prescribed prior to, during or post-operatively (including OR procedures) will be documented through study exit.

11.4.3. Cranial Nerve Physical Exam

A standard cranial nerve physical exam will be employed for all subjects enrolled for in-office procedure at screening, after the procedure and at the 3-week post-procedure follow-up visit to identify any potential adverse effects related to the lidocaine iontophoresis anesthesia component of the procedure. [REDACTED]

[REDACTED] Any abnormalities will be recorded at screening, procedure and at the follow-up visit and the subject will be assessed for any adverse events. [REDACTED]

11.4.4. Otoscopy

An otoscopic exam will be conducted for both ears in all subjects at screening, for all ears intended for treatment at procedure and for all treated at the follow-up visits. The otoscopic examination will be used to visually examine the condition of the external ear canal and TM. Routine ear cleaning may be conducted only to the extent necessary to ensure the tympanic membrane and ear canal are free from matter that may interfere with iontophoretic delivery and to ensure visualization of the tympanic membrane. Ear cleaning at the screening visit is required. Patients who are uncooperative during ear exam and ear cleaning at screening are not eligible study candidates.

The exam will be used to confirm eligibility, to assess the ear canal and TM for changes or adverse effects, and to inspect for residual drug prior to tube placement. In addition, appearance and patency of the tympanostomy tube and appearance of the myringotomy wound will be evaluated post-procedure and at the post-procedure follow-up visits. Presence or absence of middle ear effusion will be assessed.

The screening otoscopic exam may be conducted up to 28 days prior to procedure. Otoscopic examination is considered standard of care for this patient population and may be obtained prior to study informed consent as a screening assessment within 28 days prior to procedure.

11.4.5. Tympanometry

Standard tympanometry of both ears will be employed to assess TM function at screening (within 28 days prior to procedure) and at all follow-up visits for all treated ears. Tympanometry data recorded will include tympanogram type, ear canal volume, peak pressure, and static acoustic immittance as an objective measure of tube patency and middle ear status. If adequate tympanometer seal or a valid tympanogram cannot be achieved for screening tympanometry evaluation, the subject will be considered a screening failure, and will not be eligible for the study. Tympanometry is considered standard of care for this patient population and may be obtained prior to study informed consent as a screening assessment within 28 days prior to procedure.

11.4.6. Audiometry

Audiometry will be employed to evaluate hearing status in each ear at screening (within 28 days prior to procedure) and at the 3-week post-procedure follow-up visit for all subjects age 4 years or older. Threshold testing will be conducted using air conduction and bone conduction at a minimum of 500, 1000, 2000 and 4000 Hz, and air conduction only at 8000Hz. Study sites will make efforts to measure hearing thresholds at all 5 frequencies. For younger subjects (less than 4 years of age), clinical study sites will attempt to collect audiometry at screening at a minimum of two frequencies for both air conduction (AC) and bone conduction (BC). The clinical study site audiologist will determine the most appropriate test method for each subject (visual reinforcement audiometry (VRA), conditioned play audiometry (CPA) or conventional audiometry). The method used at screening will be used for all follow-up assessments.

Audiometry is considered standard of care for this patient population and may be obtained prior to study informed consent as a screening assessment within 28 days prior to procedure.

11.4.7. Anesthesia Effectiveness

Following iontophoresis, the Investigator will use physician judgment to assess whether the TM is adequately anesthetized for the tympanostomy tube placement procedure by evaluating subject response to a gentle tap of the TM with a dull otologic instrument,

The tap will occur on the anterior half of the TM at the location where the tympanostomy tube will be placed. This tap assessment method has been used successfully in prior studies to determine adequate anesthesia for subsequent tympanostomy tube placement for both children and adults.

11.4.8. Tolerability (FPS-R)

The Faces Pain Scale-Revised (FPS-R) (**Figure 10**) is an instrument for assessing procedural pain validated for use in children 4 years of age and older. This study will employ the FPS-R for children in the older cohort only (age 5 years and greater). Subjects ages 5 years and older will rate their discomfort following TDS tube placement (after second ear, if bilateral treatment) using the FPS-R. If optional suction is performed, the subject will rate their discomfort following suction of both ears (if indicated bilaterally). In addition, an FPS-R score will be collected from the children approximately 5 minutes after completion of tube placement, or after completion of suction (whichever intervention is last). A baseline measure of ear discomfort will be assessed after ear cleaning (if required) and prior to Earset placement.

[figure not shown]

Figure 10. Faces Pain Scale-Revised

If a subject discontinues the procedure prior to completion of tube placement, an FPS-R score will be collected for the discontinued procedure.

11.4.9. Tolerability (FLACC)

The FLACC (Face, Legs, Activity, Cry, Consolability) scale is a method to evaluate behavioral distress for children as young as 2 months or individuals that are unable to communicate their pain.⁶¹ The FLACC is a valid and reliable pediatric observational measure that ranges from low (0) to high (10) distress. The FLACC is recommended in the PedIMMPACT consensus statement and is a widely used observational measure of pediatric behavioral pain and distress.⁶²

The scale has five categories which are each assigned a score of 0, 1 or 2 by an evaluator, as shown in **Table 3**.

Table 3. FLACC Scoring

Category	Score 0	Score 1	Score 2
Face	No particular expression or smile	Occasional grimace or frown, withdrawn, uninterested	Frequent to constant quivering chin, clenched jaw
Legs	Normal position or relaxed	Uneasy, restless, tense	Kicking, or legs drawn up
Activity	Lying quietly, normal position, moves easily	Squirming, shifting, back and forth, tense	Arched, rigid or jerking
Cry	No cry (awake or asleep)	Moans or whimpers; occasional complaint	Crying steadily, screams or sobs, frequent complaints
Consolability	Content, relaxed	Reassured by occasional touching, hugging or being talked to, distractible	Difficult to console or comfort

FLACC scoring will be performed using the videos of the children's procedures, and will evaluate distress observed in the 6 procedural phases: pre-procedure otoscopy, iontophoresis earset installation/earset filling, iontophoresis, eardrum tap/tube placement, suction if suction is performed, post-procedure. A FLACC score will also be assigned to the overall procedure. Trained video evaluators (coders) at a centralized core lab (to ensure consistency in grading) will code a randomly selected sample of the study videos to assess interrater reliability to assess agreement across all 5 FLACC categories. █

11.5. Subject Recruitment and Informed Consent

Consecutive potentially-eligible patients presenting to the study site and for whom tympanostomy tube insertion is recommended will be offered the opportunity to participate in the study by the investigator. Subject recruitment will occur through the use of Sponsor and IRB-approved advertisements and information sheets.

The basic objective of the study, the potential benefits and risks of participating, use and protection of their personal information, and the option to not participate will be fully explained to all prospective subjects and their caregivers as specified in and in compliance with 21CFR§50, the Declaration of Helsinki, and according to the principles of ISO14155. The Investigator or delegated clinical site research staff will answer all questions to the subject's and/or subject's parent/guardian's satisfaction and will allow ample time for the subject and/or parent/guardian to read the informed consent form (and/or assent as applicable) and have additional questions answered. Subjects will be informed that the trial will be registered in the clinical trial registry databank maintained by the National Institutes of Health/National Library of Medicine (NIH/NLM). All potential subjects and/or their parent/guardian will be informed through both verbal and written information, and will sign an informed consent, or assent as applicable, according to local requirements, which states that any withdrawal from the study will neither prejudice nor in any way affect their future treatment. Subject (or legally authorized representative) consent and/or assent will be obtained in writing prior to any study-related subject data collection or procedures being performed on the subject. A copy of the completed informed consent/assent form(s) will be given to the subject and/or their parent/guardian and the original(s) will be placed in the Investigator's study record.

If new information that may affect a subject's willingness to participate or continue in the study, the Sponsor will notify the IRB and modify the informed consent and/or assent form(s) as appropriate.

All individuals that sign the informed consent, or assent as applicable, will be considered enrolled subjects.

[REDACTED]

[REDACTED]

[REDACTED]

[REDACTED]

[REDACTED]

[REDACTED]

[REDACTED]

[REDACTED]

[REDACTED]

11.6. Screening Evaluations

After written informed consent is obtained, the subject is considered enrolled in the study and will be screened for inclusion and exclusion criteria.

Screening evaluations may be conducted on day of procedure or at a separate visit up to 28 days prior to procedure. The Screening Evaluations include (in any order):

1. Medical history and concomitant/prior medications
2. Cranial nerve physical exam (in-office procedure subjects only)
3. Microscopic otoscopy with ear cleaning
4. Tympanometry and Audiometry (in either order)
5. Inclusion/Exclusion

11.7. Procedure

11.7.1. Otoscopic Examination and Ear Preparation

An otoscopic exam will be conducted using a microscope for both ears in all subjects prior to procedure. The otoscopic examination will be used to visually examine the condition of the external ear canal and TM. Routine ear cleaning may be conducted, if needed, only to the extent necessary to ensure the tympanic membrane and ear canal are free from matter that may interfere with or influence the evaluation and to ensure visualization of the tympanic membrane. Changes in concomitant medications will be recorded.

11.7.2. Earset Sizing

The IPS Earset is available in 6 sizes. The ear sizing procedure will be performed according to the Instructions for Use (IFU) provided with the IPS. If the subject's ear is not compatible with the ear plug and fit cannot be established to ensure the earplug can properly seal in the ear canal, the subject will be considered a screening failure.

11.7.3. Anesthetic Solution Preparation

The 2% lidocaine/1:100,000 epinephrine anesthetic solution will be warmed to body temperature prior to instillation of approximately 1-2mL into each ear canal to minimize the caloric effect.

11.7.4. Earset Placement and Drug Instillation

Baseline tolerability will be assessed before placement of the Earset. The Earset ear plug of the size determined in the ear sizing procedure is then placed into the ear canal. Once the ear plug is positioned, the protective liner is removed, exposing the PSA to the ear canal.

Circumferential pressure is applied through the ear plug against the surface of the ear canal, ensuring adhesion of the PSA. The Earset's integrated fill system is used to instill the selected drug into the ear canal. This process is repeated for the second ear.

The Electrode Cable is snapped to the Return Electrode Patch. The Electrode Cable connects the Earsets and the Control Unit. The Return Electrode Patch is then attached to the patient at a clean, dry site (such as the shoulder near the base of the neck) that is clear of lesions, bony protuberances and excessive hair. Prior to placing the return electrode on the patient, the investigator will assess the location for pre-existing erythema using the five point Draize erythema score where 0 indicates no erythema, 1 = very slight erythema (barely perceptible), 2 = well-defined erythema, 3= moderate to severe erythema , 4= severe erythema to slight eschar formation.⁶⁵ Category 4 also includes visible blister or burn. The location will be assessed again following iontophoresis.

In the event that drug has been introduced into the ear and iontophoresis was not initiated, the subject will return for a follow-up visit 2 to 5 days post procedure to complete all assessments required at the 3-week visit since drug will have been introduced into the ear. This subject is included in the Safety Analysis Set, but is not considered a discontinued procedure since iontophoresis was not initiated and is therefore not included in the Full Analysis Set. The subject may then be exited from the study after the follow-up visit if no unresolved device, procedure or drug-related adverse events are present. If there are unresolved adverse events, the subject must also return for the scheduled 3-week follow-up visit. However, if the subject plans to undergo tube placement in the OR, the subject's subsequent procedure success will be documented as described in **Sections 10.8.5 and 11.7.10**. This subsequent procedure must take place within 2 months of the study procedure. No additional follow-up is required following this non-study tube placement procedure.

11.7.5. Start of Iontophoresis

To begin anesthesia, the Control Unit buttons are pressed to initiate current. Initiation of current represents the beginning of the iontophoresis procedure. There are two buttons, one for each ear. Without interruptions, the Control Unit operation will take approximately 10 minutes. Progress through the iontophoresis cycle can be monitored via the progress bars on the Control Unit which fill to indicate progress toward completion.

The procedure can be paused at any time, and then resumed. The Control Unit will account for these pauses to ensure consistent current dose delivery, and will provide a visible signal when complete. The IPS 2.0 also includes a 'Reduce' feature to allow the user to optionally and temporarily reduce the current level by 25% if a subject experiences discomfort during iontophoresis. If the Reduce feature is used by the operator, the device tracks overall charge, ensuring total nominal charge/dose is delivered.

11.7.6. Anesthetic Solution and Return Electrode Patch Removal

At the end of iontophoresis, the Earset(s), and Return Electrode Patch are removed and the anesthetic solution is removed from the ear canal either by wick or head tilting. The Investigator will inspect the ear canal and TM using an operating microscope to directly visualize the anatomy confirm removal of residual drug in the ear canal.

The return electrode location will be assessed for erythema upon completion of iontophoresis and removal of the return electrode patch. Observations will be graded using the five point Draize erythema score where 0 indicates no erythema, 1 = very slight erythema (barely perceptible), 2 = well-defined erythema, 3= moderate to severe erythema, 4= severe erythema to slight eschar formation.⁶⁷ Category 4 also includes visible blister or burn. Scores of 3 or greater will be considered adverse events.

11.7.7. Post-Iontophoresis Anesthesia Effectiveness

Following iontophoresis, the Investigator will inspect the ear canal and TM using the microscope. The Investigator will then lightly tap on the anterior half of the TM (at the location where the tympanostomy tube will be placed) to evaluate subject sensation and whether anesthesia is adequate for tympanostomy tube placement. Pain resulting from inadequate anesthesia after TM tap as judged by the surgeon will be recorded as an adverse event reflecting an unacceptable level of subject discomfort that prevents the surgeon from attempting to insert the tube. [REDACTED]

[REDACTED]

[REDACTED]

[REDACTED]

[REDACTED]

[REDACTED]

[REDACTED]

11.7.8. Tympanostomy Tube Placement

The Investigator will place the TT using the TDS while the subject's head is gently stabilized by the clinic staff, as is typical for standard of care ear examinations. [REDACTED]

[REDACTED]

[REDACTED]

[REDACTED]

[REDACTED]

[REDACTED]

[REDACTED]

Following TDS tube placement, the subject will report their post-tube placement ear discomfort (on a by-subject basis) using the FPS-R.

The investigator may elect to use suction only after placement of TT in all indicated ears. A low level of suction may be used to gently remove fluid through the placed tube, taking care to not dislodge the tube. Use of suction will be recorded. Following suction, the subject will report their post-suction ear discomfort (on a by-subject basis) using the FPS-R.

Post-operative care, including otic drops, will be prescribed per investigator's discretion. All post-operative medications will be documented.

If an unexpected serious complication occurs during the procedure, the procedure will be terminated. The Investigator will take all appropriate intra- and post-treatment measures to ensure subject safety and proper treatment. The Investigator will notify Tusker Medical and their IRB immediately, but in no instances greater than 24 hours of the incident.

11.7.9. Post-Procedure Otoscopy and Cranial Nerve Exam

An otoscopic exam will be conducted post-procedure. The otoscopic examination will be used to visually examine the condition of the external ear canal, TM and tube. A cranial nerve physical exam will also be conducted pre- and post-procedure for all in-office subjects.

11.7.10. Unsuccessful Procedures

If the in-office procedure is not a success and the physician refers the subject for traditional OR TT placement, the Investigator will document the OR procedure TT placement success. Reasons for any OR procedural failures (of TT placement) will be documented. The OR procedure must take place within 2 months of the first in-office procedure. The subject must complete a post-procedure follow-up visit after the failed in-office procedure, at the protocol specified 3-week follow-up visit, or earlier if the OR procedure is planned prior to the 3-week visit. If no Tusker tube was placed, no additional follow-up visit is required following the subsequent procedure. If a Tusker tube was placed, the subject should follow the protocol-specified follow-up visit schedule to assess safety of the Tusker tube.

[REDACTED]

11.9.3-Week Post-Procedure Follow-Up Visit (+/- 7 Days)

[figure not shown]
1. All subjects are required to return for the 3-week post-procedure follow-up visit.
2. An otoscopic examination will be used to visually examine the condition of the external ear canal, TM, myringotomy, tube retention and patency.
3. The subject will complete the audiology and tympanometry, and cranial nerve physical exam (for in-office subjects only).
4. Subjects will be evaluated for any adverse events, and changes in concomitant medications will be recorded.

11.10. 6, 12, 18 and 24-month Post-Procedure Follow-Up Visits (+/- 28 days)

1. All subjects are required to return for additional follow-up visits through confirmation of tube extrusion (both ears if bilateral tube placement).
2. An otoscopic examination will be used to visually examine the condition of the external ear canal, TM, myringotomy, tube retention and patency.
3. The subject will complete tympanometry. If audiology is indicated, the study will collect audiometric data however there is no study requirement for audiology or audiology method for follow-up visits subsequent to the 3-week visit.
4. Subjects will be evaluated for any adverse events, and changes in concomitant medications will be recorded.
5. The subject will be exited from the study following confirmation of tube extrusion or completion of the 24 month visit if tube remains in place.

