	Enrollment: Up to 422, including 222 pediatric subjects in the pivotal cohort, and up to 100 lead-in OR and up to 100 lead-in in-office subjects.
Safety Measures	
Safety Evaluation will include the following assessments:
 
 • Otoscopic examination for visual inspection of external ear canal, TM condition at all visits (baseline, post-procedure and follow-up visits), with additional assessment of the myringotomy wound and tube at all protocol-specified follow-up visits. • Audiometry to assess hearing at baseline and at the 3-week post-procedure follow-up visit. • Tympanometry to assess tympanic membrane and middle ear conditions at baseline and at all protocol-specified follow-up visits. • Cranial nerve physical exam to assess cranial nerves CN VII (facial) and CN VIII (vestibulocochlear) at baseline, post-procedure and the 3-week post-procedure follow-up visit (in-office lead-in and pivotal subjects only). • Adverse events
Endpoints:	
Primary Endpoints:
 
 • Procedural Success: Proportion of subjects in the pivotal cohort with successful placement of Tusker Medical tympanostomy tubes in all indicated ears in an office procedure • Tube Placement Tolerability: Mean subject-reported pain score following TDS tube placement using the Faces Pain Scale-Revised (FPS-R) (pivotal cohort children ages 5 and older only)
	
Safety Endpoint:
 
 • Safety: Occurrence of adverse events, by subject
	
Secondary Efficacy Endpoints:
 
 • Tube Patency: Tube Patency is the proportion of subjects in the pivotal cohort, in which a Tusker Medical tube was successfully placed, with functionally patent tube(s) in all successfully treated ears at the 3-week post-procedure follow-up visit. • Tube Retention: Tube Retention is the proportion of subjects in the pivotal cohort, in which a Tusker Medical tube(s) was successfully placed, with presence of a Tusker Medical tube across the TM in all successfully treated ears at the 3-week post-procedure follow-up visit. • Anesthesia Effectiveness: Proportion of subjects in the pivotal cohort, who completed iontophoresis for all indicated ears, with adequate

anesthesia for TT placement in all treated ears as determined by physician's evaluation of TM anesthesia prior to tube placement.

Eligibility Criteria:	[REDACTED]

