11.11. Summary – Study Flow and Study Evaluations

The flow of subject participation, visits and evaluations is depicted as a schematic in **Figure 11**.

*Otoscopic examination, tympanometry and audiometry are considered standard of care for this patient population. Data obtained from these assessments within 4 weeks prior to study informed consent may be included as screening assessments.

† If tube(s) have been confirmed to have extruded, no additional follow-up visits are required and the subject may exit prior to the 24 month visit.

Figure 11. Schematic of Study Design Flow

The schedule of evaluations for each study visit is presented in **Table 4**.

Table 4. Table of Evaluations

Evaluation	Screening	Procedure	3 Weeks (-/+ 7 days)	6, 12, 18, 24 months [†] (-/+ 28 days)
Informed Consent	✓			
Medical History	✓			
Cranial Nerve Physical Exam*	✓	✓	✓	
Concomitant Medications	✓	✓	✓	✓
Inclusion/ Exclusion Criteria	✓	✓		
Otoscopy	✓ (**within 28 days prior to Procedure)	✓	✓	✓
Tympanometry	✓ (**within 28 days prior to Procedure)		✓	✓
Audiometry	✓ (**within 28 days prior to Procedure)		✓	
Procedure		✓		
Anesthesia Effectiveness*		✓		
Tube Placement Tolerability*		✓		
Suction Tolerability*		✓		
Post-Procedure Tolerability		✓		
Adverse Events		✓	✓	✓
Study Exit				✓

*Anesthesia effectiveness, cranial nerve physical exam and tolerability assessments for in-office subjects only.

** Otoscopic examination, tympanometry and audiometry are considered standard of care for this patient population. Data obtained from these assessments within 28 days prior to procedure may be included as screening assessments.

† If tube(s) have been confirmed to have extruded, no additional follow-up visits are required and the subject may exit prior to the 24 month visit.

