12.2. Serious Adverse Events

If an unexpected serious complication resulting in an adverse event occurs during the procedure, the procedure will be terminated. The Investigator will take all appropriate intra- and post-procedural measures to ensure subject safety and proper treatment. In the event of a serious adverse event at any time during the study, the Investigator will notify the Sponsor and their IRB immediately or no later than within 24 hours.

All Serious Adverse Events that have not resolved by the end of the subject's participation in the study must be followed until the event resolves, improves, or stabilizes. The investigator should report any follow-up information as it becomes available.

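### Study exit at confirmed tube extrusion does not require a closed eardrum, so a non-serious perforation seen at that visit has no required later examination

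*Protocol*

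**What the plan says.** Protocol 11.10 item 5 sets the exit rule: "The subject will be exited from the study following confirmation of tube extrusion", or after the 24-month visit if the tube is still in place. Item 1 keeps a child with bilateral tubes on the schedule until extrusion is confirmed in both ears. The footnotes to Figure 11 and Table 4 are softer. After confirmed extrusion, "no additional follow-up visits are required and the subject may exit prior to the 24 month visit". Section 11.10 is therefore mandatory where the footnotes are permissive, and neither mentions the state of the eardrum or open adverse events.

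The confirming visit is a full follow-up visit. Item 2 reads: "An otoscopic examination will be used to visually examine the condition of the external ear canal, TM, myringotomy, tube retention and patency". Tympanometry and an adverse event check are also required.

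Past exit, Protocol 12.2 provides: "All Serious Adverse Events that have not resolved by the end of the subject's participation in the study must be followed". Section 15.1 repeats this for serious events. No matching rule for non-serious events is visible.

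The safety measures in Protocol 5.0 include otoscopy "with additional assessment of the myringotomy wound and tube at all protocol-specified follow-up visits". Protocol 12.1 has the outcome and resolution date of every adverse event recorded on the case report form, and Protocol 13.6 and SAP 14.1 list outcomes. SAP 14.5 counts abnormal eardrum findings by visit. The visible SAP defines neither persistent perforation nor time to closure.

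**The concern.** The device cuts the eardrum and leaves a tube across the cut. Whether the opening closes can be judged only once the tube is out. Under 11.10 the visit that confirms extrusion is both the earliest required opportunity to judge closure and the last required examination.

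A perforation with no other consequence would not ordinarily meet the seriousness criteria in Protocol 12.3, so the follow-up in 12.2 and 15.1 would not reach it. Its outcome and resolution date would be due on the case report form, but no scheduled visit would supply them.

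At stake is the interpretation of one safety finding. An open eardrum at exit could be a cut that is still healing or one that has failed to close. The two have different implications for the safety of tube placement, and the planned data would not distinguish them.

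**Working it through.** The documents state no perforation rate, closure period or extrusion distribution, so there is no figure of the plan's own to reproduce. The check has three parts.

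**1. Who is left without a later look**

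| Situation at the confirming visit | Later examination required by visible text? |
|---|---|
| Serious event unresolved | Yes (12.2, 15.1) |
| Bilateral tubes, one out and one in place | Yes, visits continue (11.10 item 1), up to 24 months |
| Unilateral tube out, eardrum open, non-serious | No |
| Bilateral, last tube out, that eardrum open, non-serious | No |
| Tube still in place at 24 months | No; the eardrum after extrusion is never seen |

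**2. How long the tube may have been out**

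Inputs from Protocol 11.9 and 11.10: visits at 3 weeks (± 7 days), then at 6, 12, 18 and 24 months (± 28 days). One month is taken as 365.25/12 = 30.4375 days, so 6 months = 182.6 days. The tube is taken as in place at the preceding visit, with no visit missed.

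Longest gap = nominal gap + both windows.

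- 3 weeks to 6 months: 182.6 − 21 = 161.6 days nominal; longest 161.6 + 7 + 28 = 196.6, about 197 days.
- Between later visits: 182.6 days nominal; longest 182.6 + 28 + 28 = 238.6, about 239 days.

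At the confirming visit the tube may therefore have been out from 0 to about 197 days (6-month visit) or from 0 to about 239 days (later visits).

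**3. Illustration of how many confirming visits come early**

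Assume that extrusion of the tube that triggers exit is uniform within the interval. The share of confirming visits within T days of extrusion is T divided by the nominal gap. The T values are assumptions.

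| T (days) | Confirmed at 6 months (gap 161.6) | Confirmed later (gap 182.6) |
|---|---|---|
| 28 | 28/161.6 = 17% | 28/182.6 = 15% |
| 42 | 42/161.6 = 26% | 42/182.6 = 23% |
| 91 | 91/161.6 = 56% | 91/182.6 = 50% |

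These are shares of confirming visits, not of open eardrums.

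**The case against.** The strongest reply is that the plan does look. Otoscopy, tympanometry with ear canal volume, and an adverse event check all take place at the confirming visit, so an open eardrum is seen and can be recorded. Many tubes will have been out for months by then. The named safety assessment is carried out as promised. Protocol 5.0 describes the 6- to 24-month visits as assessing tube duration, and no visible endpoint promises a perforation rate.

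Most of this stands. A reader might infer that the trial cannot detect perforation at all, or that it fails a stated objective. The documents support neither. What remains is that a finding recorded as open has no required second look. The visits also have a safety role: 11.7.10 keeps a child who has a Tusker tube after an unsuccessful procedure on the schedule to assess the safety of the tube.

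A reader might also see a contradiction with Protocol 11.7.4, which lets a child given drug without current exit after an early visit "if no unresolved device, procedure or drug-related adverse events are present". The rules do not conflict. Section 11.7.4 covers different subjects, seen 2 to 5 days after the procedure, and an unresolved event only obliges them to return for the 3-week visit. It shows that the protocol can tie exit to event status, but it does not mention eardrum closure.

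Applying the 15% share to all 222 pivotal children would not measure the harm. That total includes children whose procedure failed and who may have no tube to follow, and the share counts recent extrusions. The number with an open eardrum at exit cannot be derived from the documents.

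**Conclusion.** The point holds in a narrow form. The visible exit rule is not conditional on eardrum closure or on resolution of non-serious related events. For unilateral cases and the last ear to extrude, a non-serious perforation seen at the confirming visit has no required later examination. With a possible 0 to about 197 or 0 to about 239 days since extrusion, such a finding cannot be assigned to recent extrusion or to failed closure.

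The day ranges follow from the visit schedule, given no missed visits. The shares of about 15% within 28 days and 50% within 91 days rest on assumed uniform extrusion between 6-monthly visits and on cut-offs that the documents do not supply. The number of children affected is unknown and may be small.

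The conclusion covers visible text only. Large parts of the protocol's further endpoints, safety monitoring and analysis sections, and of the SAP, are redacted and could contain a closure definition or an event follow-up rule. This is an inexpensive improvement to safety data and does not affect the primary or secondary analyses.

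**What to change.** 1. Give Protocol 11.10 item 5 and the footnotes to Figure 11 and Table 4 the same wording, so that exit on extrusion is not mandatory in one place and optional in the other.
2. Make study exit on extrusion conditional on otoscopy documenting a closed eardrum and on no unresolved device, procedure or drug-related adverse event. A child who does not meet both stays in data collection at the already-scheduled 6-monthly visits, up to the existing 24-month limit.
3. In the SAP, tabulate perforations as closed, not closed or unknown at exit. Report separately the ears still open, and the tubes still in place, at 24 months.

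This concerns study exit and data capture only, not treatment. The cost is a short wording change and, for the minority affected, one to three further scheduled visits: up to three if extrusion is confirmed at 6 months (12, 18 and 24), two at 12 months and one at 18. No new procedure is needed. Ears still open, or tubes still in place, at 24 months remain unresolved.
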